## 4 Efficacy Parameters

### 4.1 Primary Efficacy Outcome

The primary efficacy outcome is the composite of valve thrombosis and valve-related thromboembolism. The primary efficacy outcome will be analyzed using a linearized adverse event rate, measured as percentage per patient-year (%/pt-yr).

### 4.2 Secondary Efficacy Outcome

The secondary efficacy outcome is the individual components of the primary efficacy outcome of valve thrombosis and valve-related thromboembolism. The secondary efficacy outcome will be analyzed using a linearized adverse event rate, measured as %/pt-yr.

## 5 Safety Parameters

### 5.1 Primary Safety Outcome

The primary safety outcome is major bleeding and Kaplan-Meier freedom from bleeding at 2 years will be compared using a log-rank test. Major bleeding will be also analyzed using a linearized adverse event rate, measured as percentage per patient-year (%/pt-yr).

### 5.2 Secondary Safety Outcome

All secondary bleeding definitions and clinical outcomes defined in Section 7 of the study protocol, including valve thrombosis or dysfunction, stroke or TIA, myocardial infarction, arterial thromboembolism, bleeding, hospitalization and the reason for hospitalization, death and the cause of death, will be collected and be summarized with frequencies and percentages per treatment group.

## 6 Statistical Methodology

### 6.1 Statistical and Analytical Issues

#### 6.1.1 General principles

Statistical methods will be based on the International Conference on Harmonization (ICH) E9 document “Statistical Principles for Clinical Trials”. All hypothesis testing will be carried out at the 2.5% (1-sided) significance level unless otherwise specified. P-values will be rounded to three decimal places. P-values less than 0.001 will be reported as <0.001 in tables. P-values greater than 0.999 will be reported as >0.999. All statistical analysis will be performed using SAS® v9.4 or higher (Cary, NC USA).

In summary tables of continuous variables, the minimum and maximum statistics will be presented to the same number of decimal places as the original data. The arithmetic mean (AM), median (Q1, Q3), 95% confidence interval (CI), standard deviation (SD) and standard error (SE) will be presented to one more decimal place than the original data. In the event no meaningful information is available through the aforementioned decimal place, the statistician in consultation with the PI or designee will determine the most relevant number of decimals to display. Summaries of continuous characteristics will be based on non-missing observations.

In summary tables of categorical variables, counts and percentages will be used. The denominator for each percentage will be the number of patients with non-missing values for the variable within the population treatment group unless otherwise specified. In the event that the summary displayed is for a subcategory (“child”) of a main category (“parent”), the denominator for the “child” will be based on the non-missing observations for the “parent” (e.g., Heart Failure (Y/N) is a “parent” question and Heart Failure Functional Class (e.g. Class I) is a “child” question. The denominator for Class I will be number of patients who answered yes/no to the Heart Failure question).

Unless otherwise specified in this document, relative study day is defined as the (assessment date of a measurement – randomization date) if assessment date is prior to randomization date and will be defined as (assessment date of measurement – randomization date) + 1 if assessment date is on/after date of randomization. Using this derivation, the day of randomization will be considered study day 1.

Data displayed by visit will utilize an “analysis visit” which will be derived based on windowing outlined in section 6.1.2.

A baseline value is defined as the most recent assessment taken prior to/on day of randomization. When there is a missing assessment, it will not be imputed, thus, patients are excluded from any changes from baseline analysis for which they have a missing baseline value.

Due to the anticipated small number of events, stratification by site would produce sparse data and therefore, the baseline hazard within each stratum would be poorly estimated with such models. For this reason, sites will be pooled together and all Cox proportional hazards models will be adjusted for age of valve only.

Unless otherwise specified, all Kaplan-Meier rates and Kaplan-Meier curves will be performed only with the treatment group.

Case report form (CRF) data collected will be presented within data listings. The data listings will be sorted by treatment group, site number, patient number and visit.

The treatment label for all Tables, Listings and Figures will be:

Treatment	Treatment Label for TFLs
Apixaban (5 mg BID or 2.5 mg BID)	Apixaban
Warfarin (INR target range 2.0 - 3.0)	Warfarin
All Treatments	All Patients

Should any of the statistical methods proposed prove unsuitable during the final analysis, more appropriate methods will be used, and any changes will be documented in the clinical study report (CSR), including the rationale for use. These include the transformation of the data (for example to a logarithmic scale) in order to satisfy the model assumptions such as normally distributed residuals with constant variance; or the application of non-parametric techniques.

Additional ad-hoc analyses may be conducted as deemed appropriate.

#### 6.1.2 Analysis visits

Information displayed “by visit” will utilize analysis visits based on windows as opposed to the visits at which the information was collected, except baseline information. Baseline can be referred to the date of screening or Day 1 Randomization when a patient is randomized (see Section 1.1 of the study protocol). Analysis day for purposes of the visit windows are derived as follows (the reference date is the randomization date and is considered to be day 1):

- If date of information is missing, analysis day cannot be calculated
- If date of information < reference date, analysis day = analysis date – reference date
- If date of information  $\geq$  reference date, analysis day = (analysis date – reference date) + 1

The visit windows will be as follows for EQ5D and Duke Anticoagulation Satisfaction Scale obtained at month 1, 6, 12, and 24.

Analysis Visit	Analysis Visit Window	Analysis Visit Target Day
Month 1	$1 < \text{analysis day} \leq 45$	30
Month 6	$45 < \text{analysis day} \leq 270$	180
Month 12	$270 < \text{analysis day} \leq 540$	360
Month 24	$540 < \text{analysis day} \leq 900$	720

#### 6.1.3 End of study

As described in the study protocol (Section 5.8), the original plan for the end of study was defined as that time when the last patient has been followed for 2 years (that patient's 24 month visit). However,

the study has been stopped by the DSMB due to safety concerns, thus the end of study has been modified as 30 days after the last dose of study drug or the end of study date.

#### 6.1.4 Handling of Dropouts and Missing Data

For the assessment of primary hypothesis, missing data relating to the indicator for the valve thrombosis or valve thromboembolic events will not be imputed.

Any partially missing date for an adjudicated or site reported event and for termination dates at the time of database lock will be imputed as follows:

- If the day is missing, then the 1st of the month will be used.
- If missing day and month, then June 1st of provided year will be used.
- If year is missing, no imputation will be performed.

If imputation leads to a date being prior to the randomization date, it will be set to the randomization date. If imputation leads to a date being after end of study date, it will be set to the end of study date.

If study drug initiation dates are partially missed, the randomization date will be used.

If a patient is determined as lost to follow-up at the end of study, most recent date of contact where elements of the outcome of interest were assessed will be used for the last date of study.

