## 6 Study Assessments and Procedures

Study procedures and their timing are summarized in the SoA. Protocol waivers or exemptions will not be allowed. Immediate safety concerns should be discussed with the sponsor immediately upon occurrence or awareness to determine if the participant should continue or discontinue study intervention.

Adherence to the study design requirements, including those specified in the SoA, is essential and required for study conduct. All screening evaluations must be completed and reviewed to confirm that potential participants meet all eligibility criteria. The investigator will maintain a screening log to record details of all participants screened and to confirm eligibility.

Procedures conducted as part of the participant's routine clinical management and obtained before signing of the ICF may be used for screening or baseline purposes provided the procedures met the protocol-specified criteria and were performed within the time frame defined in the SoA.

The protocol includes screening participants for symptoms suggestive of valve thrombosis, such as new onset heart failure (dyspnea, edema, etc) or thromboembolic phenomena (e.g., hospitalization for stroke or urgent revascularization). This will be implemented via a standardized questionnaire at monthly intervals. Additional imaging (echocardiography, CT, MRI, angiography, and/or non-cardiac ultrasound), selected based on clinical indication, will be pursued for participants that report symptoms or signs potentially suggestive of valve thrombosis or valve-related thromboembolism. Imaging results will be collected to independently adjudicate whether or not valve thrombosis or valve-related thromboembolism occurred.

The maximum amount of blood collected from each participant over the duration of the study, including any extra assessments that may be required, will not exceed 500 mL. Repeat or unscheduled samples may be taken for safety reasons or for technical issues with the samples.

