#### 6.1.5 Time to event analysis

Unless otherwise specified in this document, time to event for the ITT population will be defined as [event date – randomization date] +1 where event occurs and as [appropriate censoring date based on analytic population – randomization date] +1 where event does not occur.

Time to event for the OT population will be defined as [event date – study drug initiation date] +1 where event occurs prior to/at 7 days after permanent study drug discontinuation and as [appropriate censoring date based on analytic population – study drug initiation date] +1 where event does not occur or occurs greater than 7 days after permanent study drug discontinuation.

Unless otherwise specified in this document, time to event for the AT population will be defined as [event date – study drug initiation date] +1 where event occurs and as [appropriate censoring date based on analytic population – study drug initiation date] +1 where event does not occur.

Treatment differences will be evaluated using a Cox proportional hazards model that includes treatment as an indicator variable and adjusted for age of valve, unless specified otherwise. The Breslow method will be used for handling ties. P-value and CI for the HR will be based on the Wald statistic. In addition, the summary tables of these analyses will include the number (%) of patients with event, Kaplan-Meier rates as well as the 95% CI by treatment monthly from randomization through the maximum follow-up. Competing risks are not taken into account for any of the Cox proportional hazards models. Competing risks may be taken into account as a sensitivity analysis if a considerable number of deaths are observed. Kaplan-Meier curves will be produced through maximum follow up available in the study, with number of patients at risk indicated below the plot at specific times.

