### 6.1.6 Censoring

In this study we expect missing outcome data to be infrequent and every effort will be made to collect all information regarding the primary outcomes through the end of the study, even in those who have discontinued the study treatment.

The censoring date for ITT analyses will be the earliest of the following: 1) most recent date of contact where the hospitalization question was assessed for the primary composite outcome or where all elements of bleeding were assessed for the primary safety outcome, including the date of a withdrawal of consent, and 2) death date (when death is not part of the outcome). Patients without any assessment of the outcome of interest will be censored at randomization.

The censoring date for AT analyses will be the earliest of the following: 1) most recent date of contact where the hospitalization question was assessed for the primary composite outcome or where all elements of bleeding were assessed for the primary safety outcome, including the date of a withdrawal of consent, and 2) death date (when death is not part of the outcome). Patients without any assessment of the outcome of interest will be censored at study drug initiation.

The censoring date for OT analysis will be the earliest of 1) most recent date of contact where the hospitalization question was assessed for the primary composite outcome or where all elements of bleeding were assessed for the primary safety outcome, including the date of a withdrawal of consent, 2) death date (when death is not part of the outcome), and 3) 7 days after the permanent discontinuation of assigned study drug. Patients without any assessment of the outcome of interest will be censored at study drug initiation.

A sensitivity analysis with the more conservative censoring date where all elements of the primary composite outcome were assessed will be performed for all three analysis populations.

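### SAP v1.4 bounds imputed dates by randomisation and study end, although as-treated and on-treatment time runs from first dose, so partial dates can give negative times or drop an on-treatment event

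*Combined protocol and SAP*

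**What the plan says.** SAP v1.4 section 6.1.4 has one rule for partial event dates and *termination dates*. Its scope is: "Any partially missing date for an adjudicated or site reported event and for termination dates at the time of database lock will be imputed". The parts of the rule are:

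- Only the day unknown: "If the day is missing, then the 1 st of the month will be used".
- Month unknown as well: "If missing day and month, then June 1 st of provided year will be used".
- Lower bound: "If imputation leads to a date being prior to the randomization date, it will be set to the randomization date".
- Upper bound: "If imputation leads to a date being after end of study date, it will be set to the end of study date".

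A partial study drug initiation date is replaced by the randomisation date. *Termination dates* is not defined, and no separate rule covers partial drug stop dates.

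Section 6.1.5 sets the time origin. ITT time starts at randomisation. For AT, the definition opens "Unless otherwise specified in this document, time to event for the AT population will be defined as" and then gives the formula used below: the event date less the date study drug was started, plus 1. OT also starts at initiation. Section 6.1.6 ends OT follow-up at the latest "7 days after the permanent discontinuation of assigned study drug", and Section 2 does not count events that occur off study drug.

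AT is the population for the primary bleeding log-rank test, timed from drug initiation (section 6.4.1). OT is one of the planned non-inferiority sensitivity analyses (section 6.8).

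**The concern.** The bounds in 6.1.4 suit only the ITT analysis. Nothing ties an imputed event date to first dose, which is where the AT and OT clocks start. Nothing ties an imputed event date and a stop date to each other, although OT depends on the gap between them.

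Two faults follow from applying the text literally:

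1. An event that truly occurred on drug can be dated before first dose. That gives a zero or negative AT time, which has no meaning in a log-rank test, and makes the event count as off drug in OT.
2. An event that made a patient stop can be dated more than 7 days after the stop and so be excluded from OT, the analysis meant to capture it.

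At stake are the validity of some records in the primary safety test and the completeness of event counts in a supporting non-inferiority analysis.

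**Working it through.** The plan gives no figure to reproduce here; the check applies its rules to dates.

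**Inputs.** Imputation rule and bounds: SAP v1.4 6.1.4. AT time = event date − initiation date + 1: 6.1.5. OT exclusion if event date > stop date + 7: Section 2 and 6.1.6. Apixaban start on day 3 for INR 2.0 to 3.0 and on day 5 for INR above 3.0 to 4.0: SAP 1.2. Randomisation is taken as day 1; if the hold is counted from the next day, each delayed start below gives a result one day more negative.

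**Check 1: AT time.** Randomised 10 March; event truly on 25 March, recorded only as March. Imputed to 1 March, then reset to 10 March.

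| Drug start | True AT time | AT time under the rule |
|---|---|---|
| 10 March (same day) | 25 − 10 + 1 = 16 | 10 − 10 + 1 = 1 |
| 12 March (day 3) | 25 − 12 + 1 = 14 | 10 − 12 + 1 = −1 |
| 14 March (day 5) | 25 − 14 + 1 = 12 | 10 − 14 + 1 = −3 |

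ITT time is 10 − 10 + 1 = 1 in every row, so the randomisation bound does protect ITT.

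The reset is not essential. Randomised 30 March, started 3 April, event 20 April with the day missing: imputed to 1 April, AT time 1 − 3 + 1 = −1.

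The 1 June rule does the same. Randomised 10 September, event 20 November with day and month missing: imputed to 1 June, reset to 10 September, AT time −1 or −3 for a day-3 or day-5 start, against true values of 70 or 68.

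**Check 2: OT exclusion.** Take each day of a 365-day year as the true date of both event and stop, well away from randomisation and study end.

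- *Event month missing, stop date known.* The event moves to 1 June and is dropped if 1 June > stop + 7, that is, for stops from 1 January to 24 May: 31 + 28 + 31 + 30 + 24 = 144 of 365 (39.5%).
- *Event date known, stop day missing, if the rule covers drug stops.* The stop moves to the 1st and the OT window closes on the 8th. Events from the 9th on are dropped: 365 − 12 × 8 = 269 of 365 (73.7%).
- *Event date known, stop month missing, same reading.* The window closes on 8 June. Events from 9 June on are dropped: 22 + 31 + 31 + 30 + 31 + 30 + 31 = 206 of 365 (56.4%).
- *Event day missing, stop date known:* 0 of 365.
- *Same part missing from both dates:* 0 of 365.

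**Check 3: what one lost event does.** The design assumptions (500 per arm, 1.75%/pt-yr, 1-year accrual with half enrolled by 40% of it, 2-year minimum follow-up, loss hazard 0.026) give about 1,206 pt-yr and 0.0175 × 1,206 = 21 events per arm. With the SAP 6.3.1 interval, the upper bound at 21 against 21 events is 1.96 × √42 / 1,206 = 1.05%/pt-yr. With one apixaban event lost it is (−1 + 1.96 × √41) / 1,206 = 0.96%/pt-yr. The margin is 1.75%/pt-yr.

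**The case against.** The strongest counter-argument is that the rule seldom bites. Major bleeding is defined by outcomes such as death, hospitalisation, transfusion or reoperation, which usually leave dated records. Patients are followed closely: for valve thrombosis and thromboembolic symptoms, "This will be implemented via a standardized questionnaire at monthly intervals" (protocol section 6), and the schedule has a monthly call about dosing changes. SAP 6.1.6 expects missing outcome data to be infrequent, and protocol 5.9.1 expects permanent discontinuation only in rare instances. A negative AT time also needs a known drug start later than the imputed event date. The bleeding test is repeated in ITT (SAP 6.8), where negative times cannot arise. All of this stands and limits the size; none of it makes the rule correct when a partial date does occur.

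A reader might infer more than the documents support:

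- *That the rule drops about three quarters of the events that caused a stop.* The 269 of 365 figure needs *termination dates* to mean drug stops. The SAP elsewhere calls these discontinuation, and 6.1.4 otherwise speaks of the end of study, so study termination is at least as natural a reading. The figure also applies only to pairs with a known event date and a missing stop day.
- *That every partial date is moved back.* The 1 June rule moves January to May dates forward.
- *That invalid times arise only on apixaban.* Only that arm has a planned warfarin hold, but no text says study warfarin starts on the day of randomisation. Any patient starting later is exposed.
- *That the loss favours apixaban in OT.* Protocol 5.9 describes apixaban patients returning to warfarin after an event, but equally allows continuing or pausing, and 5.9.1 covers stopping either drug. The direction is possible but not established.

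**Conclusion.** The point holds as a minor defect. The lower bound in SAP v1.4 6.1.4 does not match the AT and OT time origin, and taken literally it gives AT times of −1 or −3 days in the primary safety log-rank test. This needs no disputed reading, only a partial event date and a known later drug start. It arises mainly, not exclusively, in the apixaban arm.

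Loss from OT of an event that led to a stop is also real. It occurs when the event month is missing and 1 June falls more than 7 days after the known stop (144 of 365 same-day pairs). It occurs for a missing stop day (269 of 365) only if *termination dates* covers drug stops. These shares assume dates spread evenly over the year and event and stop on the same day.

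The ITT co-primary analysis is unaffected. The frequency of partial dates is not given, so the total effect cannot be sized and is probably small. One lost apixaban event would lower the OT upper bound by about 0.1%/pt-yr under the full planned follow-up, which the early stop recorded in SAP 6.1.3 makes an optimistic exposure figure.

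**What to change.** Amend SAP v1.4 section 6.1.4 as follows:

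1. For AT and OT, an imputed event date may not be earlier than study drug initiation when the event was reported as occurring after first dose.
2. State whether *termination dates* includes study drug discontinuation; if it does not, give a rule for partial stop dates. In either case, do not impute a stop earlier than the last date recorded on drug, or earlier than an event recorded as the reason for stopping. Do not impute such an event later than the known date of the stop it caused.

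In the examples above, the smallest AT time becomes 12 − 12 + 1 = 1 day, and 0 of 365 same-day event and stop pairs are dropped.

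The cost is a few sentences and a few lines of programming. Patients with partial stop dates would gain slightly longer OT exposure. Placing event dates midway between bracketing contacts, or stop dates at the end of the month, is optional and not needed to correct the error; end-of-month stops could attribute off-drug events to the assigned drug.

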#### 6.1.5 Time to event analysis

Unless otherwise specified in this document, time to event for the ITT population will be defined as [event date – randomization date] +1 where event occurs and as [appropriate censoring date based on analytic population – randomization date] +1 where event does not occur.

Time to event for the OT population will be defined as [event date – study drug initiation date] +1 where event occurs prior to/at 7 days after permanent study drug discontinuation and as [appropriate censoring date based on analytic population – study drug initiation date] +1 where event does not occur or occurs greater than 7 days after permanent study drug discontinuation.

Unless otherwise specified in this document, time to event for the AT population will be defined as [event date – study drug initiation date] +1 where event occurs and as [appropriate censoring date based on analytic population – study drug initiation date] +1 where event does not occur.

Treatment differences will be evaluated using a Cox proportional hazards model that includes treatment as an indicator variable and adjusted for age of valve, unless specified otherwise. The Breslow method will be used for handling ties. P-value and CI for the HR will be based on the Wald statistic. In addition, the summary tables of these analyses will include the number (%) of patients with event, Kaplan-Meier rates as well as the 95% CI by treatment monthly from randomization through the maximum follow-up. Competing risks are not taken into account for any of the Cox proportional hazards models. Competing risks may be taken into account as a sensitivity analysis if a considerable number of deaths are observed. Kaplan-Meier curves will be produced through maximum follow up available in the study, with number of patients at risk indicated below the plot at specific times.

